12.1.1. Primary Endpoint

The primary endpoint is an assessment of improvement in pelvic organ prolapse severity at 36 months as compared to Baseline.

12.1.1.1. Hypotheses

Non-inferiority testing for effectiveness will be performed for the primary hypothesis.

Statistical testing will be performed to determine if composite endpoint of anatomic and symptomatic success rate in transvaginal biologic mesh repair (treatment) group will be non-inferior to traditional native tissue repair (control) group. The null hypothesis is that the success rate in treatment group is less than or equal to the success rate in control group minus margin:

$$H_0: \pi_{treatment} - \pi_{control} \leq -\Delta$$

The alternative hypothesis is:

$$H_a: \pi_{treatment} - \pi_{control} > -\Delta$$

where $\pi_{treatment}$ and $\pi_{control}$ are the probability of success in the treatment group and control group respectively, and $\Delta > 0$ is defined as the non-inferiority margin.

Statistical testing will be performed to determine if the overall complication rate (i.e., serious device-related or serious procedure-related adverse events) of treatment group is non-inferior to the control group. The null hypothesis is that the complication rate in treatment group is greater than or equal to the rate in control group plus margin:

$$H_0: \pi_{treatment} - \pi_{control} \geq \Delta$$

The alternative hypothesis is:

$$H_a: \pi_{treatment} - \pi_{control} < \Delta$$

where $\pi_{treatment}$ and $\pi_{control}$ are the overall complication rate in treatment group and control group respectively, and $\Delta > 0$ is defined as the non-inferiority margin.

12.1.1.2. Sample Size

The statistical power calculation is based on a non-inferiority assumption with a binary primary outcome. Objective success, based on a composite endpoint of anatomic and symptomatic success at 36 month is assumed to be 70.0%^{5-8, 16} for the native tissue arm. With type I error of 0.05 and type II error of 0.20 (power 80%), 362 subjects (181 subjects per arm) are needed to detect non-inferiority of transvaginal biologic to native tissue repair, using a margin of 12.0%.

To assess for safety, the overall complication rate (i.e., serious device-related or serious procedure-related adverse events) is anticipated to be approximately 14% per arm.⁹ With type I error of 0.05 and type II error of 0.10 (power 90%), 308 subjects (154 subjects per arm) are needed to detect non-inferiority with a margin of 11.6%.

To assess for office-based interventions for complications, the rate is anticipated to be approximately 2%.⁹ With type I error of 0.025 and type II error of 0.10 (power 90%), 330 subjects (165 subjects per arm) are needed to detect non-inferiority with a margin of 5%.

To assess for of surgical intervention for complications, the rate is anticipated to be approximately 1%.⁹ With type I error of 0.025 and type II error of 0.10 (power 90%), 260 subjects (130 subjects per arm) are needed to detect non-inferiority with a margin of 4%.

Non-surgical subjects will not be enrolled into this clinical study as all data on this cohort of subjects will be obtained from the AUGS Pelvic Floor Disorders Registry under Level 2 and analyzed with data from this clinical study.

Using the above calculations and assuming a 20% loss to follow-up rate, a total of 454 subjects (227 per study arm) will be enrolled to achieve the primary endpoint of success at 36 months.

12.1.1.3. Statistical Methods

For the primary effectiveness endpoint, non-inferiority will be evaluated using a two-sided 90% confidence interval for the treatment difference (Xenform minus native tissue repair). If the entire confidence interval is above the margin (i.e., -12%), non-inferiority will be demonstrated. The confidence interval will be calculated based on the pooling of treatment differences across propensity score strata for a binary endpoint, as described in Section 12.2.3 (Propensity Score Methodology).

If any data on the primary efficacy endpoint is missing, multiple imputation will be performed in which the missing values will be imputed five times under a logistic distribution model, using a fully conditional specification that includes the treatment arm and the assessments of the treatment success endpoint at each of 2, 6, 12, 18, and 24 months. As

a sensitivity analysis, the comparison of treatments will also be performed using the following methods:

- Tipping point analysis
- Available cases only (i.e., only the subjects for whom the endpoint was assessed)

For the primary safety endpoint, the proportions will be calculated using for the numerator the number of subjects with an endpoint event and for the denominator the number of subjects in the analysis population (ITT and Per Protocol group). Non-inferiority will be evaluated using a two-sided 90% confidence interval for the treatment difference (Xenform minus native tissue repair). If the entire confidence interval is below the margin (i.e., 11.6%), non-inferiority will be demonstrated. The confidence interval will be calculated based on the pooling of treatment differences across propensity score strata for a binary endpoint, as described in Section 12.2.3 (Propensity Score Methodology).

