12.3.8.2. Statistical Methods

The comparisons of transvaginal biologic mesh repair to native tissue repair will be based on a two-sided 90% confidence interval for the treatment difference. The confidence interval will be calculated based on the pooling of treatment differences across propensity score strata for a binary endpoint, as described in Section 12.2.3 (Propensity Score Methodology).

² To support the continued review of the Premarket Approval Application for the United States, Boston Scientific will submit hypothesis testing as an Amendment to the initial PMA following acceptance and filing.

Missing 12 month data for the composite efficacy endpoint will be handled by multiple imputation under a logistic regression model using a fully conditional specification. The imputation model will include treatment group and primary efficacy outcome at 2 and 6 month. A total of 5 imputed data sets will be generated.

The following methods will also be used as sensitivity analyses:

- Tipping point analysis
- Observed data only

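### Five imputations for about 20% missing primary outcomes leave the non-inferiority verdict poorly reproducible: two random seeds disagree in about 5-8.5% of trials at the design assumptions

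*Combined protocol and SAP*

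**What the plan says.** For the primary effectiveness endpoint, Section 12.1.1.3 states that "the missing values will be imputed five times under a logistic distribution model". The imputation model is of the chained-equations type, described there as a "specification that includes the treatment arm and the assessments of the treatment success endpoint at each of 2, 6, 12, 18, and 24 months". Non-inferiority is declared if the whole two-sided 90% interval for Xenform minus native tissue lies above -12%. The interval pools differences over the five propensity strata of Section 12.2.3. The sensitivity analyses listed are a tipping-point analysis and an available-case analysis.

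Section 12.1.1.2 sets the scale of the missing data: "assuming a 20% loss to follow-up rate, a total of 454 subjects (227 per study arm) will be enrolled". Sections 10.2.5 and 12.2.1 keep withdrawn subjects in the ITT analysis, so their outcomes have to be imputed.

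The 12-month interim tests use the same number: "A total of 5 imputed data sets will be generated" (Section 12.3.8.2).

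Neither section gives a random seed, a reason for five, or a limit on Monte Carlo error.

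**The concern.** Multiple imputation draws the missing outcomes at random, so its result changes with the seed. The change shrinks as the number of imputations, m, grows. With m = 5 and a fifth of outcomes missing, both the pooled estimate and its estimated variance carry noise that has nothing to do with the patients.

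That noise would matter little in a descriptive estimate. Here one limit is compared with one fixed number, so two analysts who follow the same plan on the same data can reach opposite conclusions on the primary endpoint. The listed sensitivity analyses do not measure this, because they address why data are missing and not the randomness of the draws. An unspecified seed also leaves a borderline result open to challenge.

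**Working it through.** **Inputs.** From Section 12.1.1.2: 70% control success, margin 12 points, type I error 0.05, power 80%, 20% loss. From Section 12.1.1.3: m = 5 and the 90% interval. Assumed: 70% in the Xenform arm, 20% of primary outcomes missing at random, Rubin's rules for combining (the section names no rule), and the predictive strength of earlier visits.

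**1. The plan's own figure.** n per arm = (1.645 + 0.842)² × 2(0.7)(0.3) / 0.12² = 180.3, so 181. This matches "With type I error of 0.05 and type II error of 0.20 (power 80%), 362 subjects (181 subjects per arm) are needed" and shows that 0.05 is one-sided and that equal success rates were assumed. 181/0.8 = 226.25, so 227 per arm and 454 in total. About 0.20 × 227 = 45 outcomes per arm would be imputed.

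**2. Noise in the limit, by hand.** Complete-data variance W = 0.42/227 = 0.00185. If the fraction of missing information is g, the large-m total variance is W/(1 - g) and the between-imputation variance is B = W·g/(1 - g). With no help from earlier visits g = 0.20. With a correlation of 0.5 between one earlier outcome and month 36, simulation gives g = 0.157.

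- Seed SD of the estimate = √(B/m).
- Seed SD of the limit from the estimated variance ≈ t × (1 + 1/m) × B × √(2/(m - 1)) / (2√T), with T = W + (1 + 1/m)B.

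| m = 5 | g = 0.20 | g = 0.157 |
|---|---|---|
| B | 0.000463 | 0.000345 |
| √(B/5), points | 0.96 | 0.83 |
| from the variance estimate, points | 0.67 | 0.51 |
| combined SD of the limit, points | 1.17 | 0.97 |

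Stronger prediction lowers this to about 0.8 in simulation. At m = 100 the same formulas give 0.24 and 0.20.

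**3. From noise to disagreement.** The chance that two seeds fall on opposite sides of -12% is roughly the density of the limit at -12% times the mean absolute gap between two seeds, 2 × SD/√π.

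- g = 0.157: the limit is centred 4.11 points above -12% and its sampling SD is 4.68 points, so the density is 0.0579 per point. The mean gap is 1.128 × 0.97 = 1.10 points. Product: 6.4%.
- g = 0.20: 0.0604 × 1.32 = 8.0%.
- m = 100: 1.3% and 1.6%.

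**4. Simulation.** 227 per arm, 70%/70%, 20% missing, and each incomplete trial re-imputed with independent seeds. With one earlier binary outcome, arm, and t limits (20,000 trials per setting at m = 5 and 20; 8,000 at m = 50 and 100), two-seed disagreement was:

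| Correlation with month 36 | m = 5 | m = 20 | m = 50 | m = 100 |
|---|---|---|---|---|
| 0 | 8.5% | 3.4% | 2.2% | 1.6% |
| 0.3 | 7.5% | | | |
| 0.5 | 6.4% | 2.9% | 1.8% | 1.3% |
| 0.7 | 4.9% | | | |

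A six-visit model with monotone dropout and sequential logistic imputation gave 5.3% to 7.6% at m = 5 without strata and 5.4% to 8.4% with five strata (standard errors 0.5 to 0.8 points). At m = 50 it gave 2.5% (standard error 1.0).

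**5. Error rates.** At a true difference of -12 points, non-inferiority was declared in 5.0% to 5.1% of trials with m = 5. Power at a true difference of 0 rose from 78.7% (m = 5) to 80.5% (m = 50) with correlation 0, and from 80.5% to 82.0% with correlation 0.5.

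**6. Other settings at m = 5** (correlation 0 / 0.5).

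- True difference of -8 points: 7.4% / 6.6%; -4: 11.1% / 9.5%; +4: 2.9% / 1.9%; +8: 0.3% / 0.2%.
- Missing 10%: 4.7% / 3.6%; 25%: 10.4% / 8.4%; 30%: 12.8% / 10.3%.

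**The case against.** The strongest defence is that the plan remains valid. Rubin's rules add B/m to the variance, and t limits allow for B being estimated from only five values, which is why type I error stays at 5%. The noise is also small beside sampling error: with 181 evaluable per arm the standard error is √(0.42/181) = 4.8 points, and adding 1.1 points of seed noise raises it only to √(4.8² + 1.1²) = 4.9. Seeds change the verdict mainly when the limit already lies within a point or two of -12%, and the available-case analysis, which uses no random draws, would sit beside it. All of this stands. It bears on how serious the point is, but it is no reason to keep avoidable noise in a decision limit.

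A second objection is that 20% is a loss-to-follow-up rate, not the share of composites to be imputed. That also stands, in both directions. A known failure on one component settles the composite without a visit (Section 7.1), whereas telephone visits with mailed questionnaires (Section 11.4.5) leave POP-Q missing.

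Three stronger readings are tempting, and the documents do not support them:

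- A reader might infer that a fixed share of trials, such as 7% or 8%, has a seed-dependent verdict. The figure is the chance that two seeds disagree. It moves with the true difference, the missing fraction and a visit-to-visit correlation that the documents do not give. The share of simulated trials in which six seeds were not unanimous is a different quantity, 12% to 19%.
- A reader might infer bias or an inflated false-positive rate. Step 5 of the working shows neither.
- A reader might carry the same figures over to the 12-month interim. Section 12.3.8.2 uses only months 2 and 6 as predictors, and the plan gives no 12-month missing rate, so the effect there has not been sized.

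**Conclusion.** The point holds as a matter of reproducibility and a small loss of precision. The 5% to 8.5% disagreement at the design point assumes a true difference of 0, 20% missing at random and Rubin's rules. Its lower end corresponds to earlier visits that predict month 36 strongly, its upper end to no prediction. Disagreement is highest, about 9.5% to 11%, when the true difference is near -4 points and the verdict is in real doubt. It is below 1% when Xenform is 8 points better. Because error rates are sound, this is a recommended improvement and does not undermine the analysis.

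**What to change.** In Section 12.1.1.3, replace five with 100 imputations (at least 50) and state the random seed. Both parts are needed: a fixed seed makes the reported result repeatable but leaves the noise in it, while more imputations remove most of the noise. Even 100 imputations leave about 1% to 2% disagreement. Make the same change in Section 12.3.8.2 so that the two analyses match.

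No new data, change of sample size or change of imputation model is required. Computing takes a few minutes. Section 14 requires approvals before a protocol revision is implemented, so the edit is best bundled with the next protocol or SAP revision. The current revision is dated March 2018 and database lock is expected in February 2020 (Table 10.1-1), which leaves room to do this before the final analysis.

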11.4.5. Follow-Up

Subjects will be scheduled for follow-up visits as outlined in Table 11.1-1 (Data Collection Schedule). The follow-up visit schedule begins from the day of the study surgery and includes visit windows (counted in calendar days).

Every effort should be made to do the follow-up visit within the window; however, if this is not possible, the site should attempt to complete the visit as soon as possible but before the next visit window opens. Follow-up visits will be considered missed once the visit window for the next follow-up visit opens. For the Month 36 visit, the visit is not considered missed until the last day of the visit window (i.e., +12 weeks).

Every effort should be made to conduct the follow-up visit at the study site location. However, if the subject cannot physically return to the site for any reason, the follow-up visit may be conducted at the subject's home with their consent and if allowed by local institutional policy and the IRB/EC. If a home visit is not possible, every effort should be made to conduct as much of the visit as possible by phone (i.e., assess adverse events, risk factors, and analgesic intake) and to send the subject questionnaires by mail for completion.

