12.2.2. Control of Systematic Error/Bias

To reduce selection bias in this non-randomized study, each study center will be permitted to enroll subjects in only one of the treatment groups. Physicians will be selected based on device and clinical research experience and the decision as to which device to implant in subjects prior to study initiation at each center. Some study centers may be permitted per Boston Scientific to enroll subjects in both treatment and control groups. All decisions will be documented prior to subject enrollment. All subjects meeting the eligibility criteria at the study center will be screened and enrolled as applicable.

Propensity score stratification will be utilized to address the potential imbalance in risk factors between groups, described in Section 12.2.3 (Propensity Score Methodology). This analysis will be performed blind to all clinical outcome data and prior to performing any analysis of endpoints.

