12.2.3. Propensity Score Methodology

Analyses comparing the treatment groups will be adjusted for the propensity score. The propensity score is the probability that the subject enrolled in the mesh arm rather than the native tissue (control) arm, given the characteristics of the subject and center. The characteristics identified are as follows: age, race, body mass index, smoking, diabetes, post-menopausal, prior prolapse repair, prior hysterectomy, estrogen use, POP-Q C measurement, POP-Q Ba measurement, POP-Q Bp measurement, concomitant repair for stress urinary incontinence, and surgeon case volume. Logistic regression of both treatment arms (i.e., (transvaginal biologic mesh repair vs. native tissue repair) on these characteristics will be used to estimate the propensity score. The subjects will then be partitioned into five strata corresponding to quintiles of the propensity score. If the balance between treatment arms within the strata is deemed adequate, the treatment difference adjusted for propensity score stratum will be estimated as described in the following.

The propensity adjusted treatment difference will be based on averaging the treatment differences of the propensity score strata. For a binary outcome, the within-stratum treatment difference is $D_j = p_{T_j} - p_{C_j}$, where p_{T_j} and p_{C_j} is the proportion of treatment and control subjects, respectively, in stratum j . The variance of D_j is approximately

$$V_j = \frac{p_{T_j}(1 - p_{T_j})}{n_{T_j}} + \frac{p_{C_j}(1 - p_{C_j})}{n_{C_j}}$$

Denoting the number of subjects in stratum j by $n_j = n_{T_j} + n_{C_j}$, the treatment difference will be estimated by the (weighted) mean of the within-stratum treatment differences

$$D = \sum_j \frac{n_j}{n} D_j$$

where $n = \sum_j n_j$ is the total sample size across all strata and study arms. D is approximately normally distributed with variance

$$V = \sum_j \left(\frac{n_j}{n}\right)^2 V_j$$

from which a confidence interval for the true treatment difference will be constructed. For each continuous outcome, the confidence interval will be constructed similarly, with D and V obtained as above with the treatment difference within each stratum replaced by $D_j = \bar{X}_{T_j} - \bar{X}_{C_j}$, where \bar{X}_{T_j} and \bar{X}_{C_j} , respectively, is the mean of the treatment and control subjects, and

$$V_j = \frac{S_{T_j}^2}{n_{T_j}} + \frac{S_{C_j}^2}{n_{C_j}}$$

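### The imputation models for the Month 36 and Month 12 composite name treatment arm and earlier success, but not the propensity score on which the comparison is stratified

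*Combined protocol and SAP*

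**What the plan says.** **Imputation, Month 36 (Section 12.1.1.3).** Missing values of the composite are "imputed five times under a logistic distribution model, using a fully conditional specification that includes the treatment arm and the assessments" of treatment success at Months 2, 6, 12, 18 and 24. No propensity score, stratum or baseline characteristic is named.

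**Imputation, Month 12 interim (Section 12.3.8.2).** "The imputation model will include treatment group and primary efficacy outcome at 2 and 6 month". The same section adds: "A total of 5 imputed data sets will be generated".

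**Analysis, both time points.** "The confidence interval will be calculated based on the pooling of treatment differences across propensity score strata for a binary endpoint" (Section 12.1.1.3, repeated in 12.3.8.2). Section 12.2.3 estimates the score from 14 subject and surgeon characteristics, and then: "The subjects will then be partitioned into five strata corresponding to quintiles of the propensity score". Section 12.2.3 describes the comparison. It does not mention imputation.

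**Expected missing data.** Section 12.1.1.2 plans for it: "assuming a 20% loss to follow-up rate, a total of 454 subjects (227 per study arm) will be enrolled". Section 11.4.5 adds a second source. If a subject cannot attend and a home visit is not possible, "every effort should be made to conduct as much of the visit as possible by phone". A phone contact gives no POP-Q measurement.

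**Sensitivity analyses.** Section 12.1.1.3 lists a tipping-point analysis and an analysis restricted to subjects with an observed endpoint.

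**The concern.** Allocation follows centre and physician (Sections 8.2, 10.1 and 12.2.2), so the propensity score is the plan's main statistical control for confounding. If the imputation model lacks the score, an imputed outcome depends on the stratum only so far as earlier success carries that information. The rest of the stratum effect is lost. Subjects who leave early have few or no earlier assessments to carry it.

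For the imputed subjects the adjustment is therefore partly reversed. The primary decision compares one confidence limit with -12%. A bias toward the crude difference can make a false claim of non-inferiority more likely if confounding favours Xenform, or cost power if it works against Xenform. A larger sample does not remove it.

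**Working it through.** **1. The plan's own figures.** Success 70% in both arms, margin 12 points, one-sided 0.05, power 80%:

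n = (1.645 + 0.842)² × 2 × 0.70 × 0.30 / 0.12² = 180.3, so 181 per arm. 181 / 0.80 = 226.3, so 227 per arm and 454 in total. Both agree with Section 12.1.1.2.

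With 0.80 × 227 = 181.6 observed per arm, the standard error of the difference is √(2 × 0.21 / 181.6) = 4.8 points, so about 5.

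**2. Upper limit of the shift.** Let a fraction f be missing at random, with no help from earlier visits and an imputation model that ignores the stratum. The imputed success rate in an arm is then the same in every stratum, and the pooled estimate becomes

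(1 - f) × adjusted + f × crude = adjusted + f × (crude - adjusted).

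At f = 0.20 the ceiling is 0.20 × 2 = 0.4 points for a gap of 2, and 0.20 × 10 = 2.0 points for a gap of 10.

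**3. Simulation of the planned Month 36 model.** The gap is an assumption throughout.
- n = 454, control success 70%, visits at Months 2, 6, 12, 18, 24 and 36.
- One normal confounder drives arm and success, with log-odds per SD of 0.4/0.3 (weak), 0.6/0.5 (moderate) and 1.0/0.8 (strong).
- Subject effect SD of 1 or 2 on the logit scale.
- Random monotone dropout reaching 20%, either spread over visits or all at Month 36.
- Sequential logistic imputation with 50 imputations, the Section 12.2.3 estimator, Rubin's rules and a 90% interval.
- 1000 to 1200 datasets per setting.

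| Confounding | Gap (points) | Shift from leaving the score out (points) |
|---|---|---|
| Weak | 1.3-1.8 | 0.1-0.3 |
| Moderate | 3.2-4.3 | 0.2-0.6 |
| Strong | 7.4-9.9 | 0.4-1.3 |

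This is 5% to 16% of the gap, below the 20% ceiling. With the propensity logit included, the estimate was within 0.1 point of the full-data estimate. A repeat gave 0.08-0.25 points at gaps of 1.4-1.8, 0.22-0.57 at 3.2-4.2, and 1.37 at a gap of 10.0.

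A differently built simulation used 455 subjects, one earlier outcome, five imputations and larger assumed confounding. It gave 0.5 to 2.2 points without the stratum and -0.13 to +0.15 with it (simulation error about 0.1).

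At 10% missing the shift was 0.15-0.6 points at Month 36. With the interim model and an assumed 10% missing at Month 12 it was 0.2-0.8. Both ranges cover moderate to strong confounding. At the weak gap the shift was about 0.04-0.2.

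**4. Effect on the decision.** These results are for the less favourable setting: dropout spread over visits and weaker within-subject correlation.

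| True difference | Confounding | Non-inferiority concluded, without / with score | Paired change, points (SE) |
|---|---|---|---|
| -12, favouring Xenform | Weak | 6.9% / 6.2% | +0.7 (0.2) |
| | Moderate | 7.8% / 6.5% | +1.3 (0.2) |
| | Strong | 10.4% / 6.4% | +4.0 (0.4) |
| 0, against Xenform | Moderate | 71% / 75% | -3.7 (0.6) |
| | Strong | 60% / 69% | -9.4 (0.9) |

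For the favourable end, take the smallest shifts in step 3 and Φ(z + shift/5), where z gives the with-score rate:
- weak: Φ(-1.538 + 0.1/5) = 6.5%
- moderate: Φ(-1.514 + 0.2/5) = 7.0%
- strong: Φ(-1.522 + 0.4/5) = 7.5%

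**5. Secondary: number of imputations.** This concerns repeatability, not bias. If earlier visits do not help, the between-imputation variance is

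B = 2f²p(1-p)[1/(fn) + 1/((1-f)n)], with f = 0.20, p = 0.70 and n = 227, which gives 0.000463.

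The Monte Carlo error of the estimate is √(B/5) = 0.96 points with 5 imputations, √(B/20) = 0.48 with 20 and √(B/50) = 0.30 with 50. Neither section states a seed.

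**The case against.** The strongest objection is size. At weak to moderate confounding the shift is at most 0.6 points, against a 12-point margin and a standard error of about 5. The larger decision effects need a gap of 7.4 to 9.9 points, and nothing in the documents shows one. In the simulation the false-claim rate is 6.2% to 6.5% even with the score included. At weak and moderate confounding that excess over 5% (1.2 to 1.5 points) is at least as large as the part due to imputation (0.7 to 1.3). All this stands, and only the paired differences are attributed to the imputation model.

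The simulation also flatters the fix. A single confounder is fully captured by the logit, whereas the real score combines 14 characteristics. It used 50 imputations where the plan has five. So the residual of 0.1 point is a best case.

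The wording does not say that the listed predictors are the only ones, and the synopsis refers to a Statistical Analysis Plan. No separate SAP text is in the combined document, and none of its sections adds the score. If the SAP does, the matter reduces to aligning the text.

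The sensitivity analyses give some protection. Under random dropout the observed-case comparison is free of this bias. A mailed PFDI-20 or a known retreatment can also settle failure without POP-Q. But the sensitivity analyses can only reveal the problem. The imputed analysis remains the primary one.

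**Conclusion.** The concern holds. At both time points the stated imputation model omits the variable on which the comparison is stratified, in a study where that variable carries the control of confounding. The resulting bias is toward the crude difference and is bounded by the missing fraction times the crude-minus-adjusted gap.

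It is negligible under weak confounding and about a quarter of a standard error (1.3/5) at the strong end. It could change the conclusion only if the limit lies close to the margin. The sizes rest on an assumed gap, on random dropout, and on 20% missing at Month 36. The change should be made because the shift cannot be predicted in size or sign, and the variable that removes it is already to hand.

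**What to change.** In Sections 12.1.1.3 and 12.3.8.2, add the estimated propensity score (logit scale) or its stratum to the imputation predictors. Use the same model for any imputation behind the tipping-point analysis. The continuous logit avoids the sparse cells that quintile indicators can produce. If the separate SAP already includes the score, confirm this and align the protocol. Keep both sensitivity analyses.

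As a secondary matter, raise the number of imputations (for example to 50) and fix the seed in advance. The larger number reduces Monte Carlo error; the seed only makes the result repeatable.

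The work is a line of text in each section and minutes of computing. No new data are needed. Section 12.2.2 already has the propensity step done before the endpoints are analysed: "This analysis will be performed blind to all clinical outcome data and prior to performing any analysis of endpoints". The formal cost is an amendment with its approvals under Section 14. For the interim this may be the larger part, since the revision history says that FDA requested those details.
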